### **9.3. Analysis of Secondary Endpoints**

As secondary endpoints, the study will investigate oncologic outcomes of the prescribed protocol therapy including biochemical progression-free survival, distant metastasis-free survival, cause specific survival, and overall survival. Kaplan-Meier curves will be generated for each endpoint. Findings will be compared to a synchronous cohort of controls.

Biochemical progression free survival will be defined to be the time from the start of therapy with oral androgen manipulation until PSA failure occurs as defined by the Phoenix definition of a rise to 2 ng/ml above the nadir PSA value. The relative hazard for a PSA failure in patients on protocol therapy compared to those in the control cohort will be calculated using the proportional hazards regression model of Cox, but formal statistical conclusions will not be drawn from this analysis.

Hematologic effects of dual oral androgen manipulation will be assessed using hemoglobin levels from scheduled CBC's. Changes in mean hemoglobin between baseline and various time points throughout treatment will be assessed. Univariate analysis of mean scores will be performed using a two sample t-test.

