## **1. OBJECTIVES**

### **1.1. Primary Objectives**

The broad objective is to test the feasibility of delivering dual oral androgen manipulation with an antiandrogen and a 5-alpha reductase (5AR) inhibitor in conjunction with dose-escalated radiation (RT) in intermediate and high risk prostate cancer patients 70 years of age or older and/or with moderate to severe medical comorbidities. The primary objective is to test the hypothesis that health-related quality of life (HRQOL) in patients treated with dual oral androgen manipulation will be improved compared to that of controls treated with standard androgen deprivation therapy (ADT) including a gonadotropin releasing hormone (GnRH) agonist +/- an antiandrogen.

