## **2. BACKGROUND**

### **2.1. Intermediate and High Risk Prostate Adenocarcinoma**

Prostate cancer is the most common non-dermatologic malignancy and the second leading cause of cancer-related death in men in the United States. In 2010, an estimated 217,730 men will be diagnosed with prostate cancer, and 32,050 will die of their disease.[1] Prostate cancer is predominately a disease affecting older men, with 75% of cases diagnosed in men aged 65 and older.[2] Despite a trend toward earlier stage at diagnosis with the widespread use of prostate specific antigen (PSA) screening, a significant percentage of patients are diagnosed with advanced disease. In an analysis of over 10,800 men with prostate cancer diagnosed between 1990 and 2007, over 50% of patients entering the cohort between 2004 and 2007 were diagnosed with intermediate or high risk prostate cancer. [3]

Multiple treatment options exists for intermediate and high risk prostate cancer ranging from active surveillance to aggressive combined modality therapy with surgery and/or radiation with or without androgen deprivation therapy (ADT). Treatment decisions involve consideration of disease features including clinical T stage, PSA, and Gleason score. In addition, the therapeutic approach should take into account comorbidities, quality of life concerns, and patient preferences.

Therapeutic decision-making can be particularly complicated in men with a limited life expectancy. In these cases, weighing the oncologic benefits of treatment against the possibility of toxicity related to a given therapy is clouded by competing risks of mortality related to comorbid illnesses and aging. The majority of patients with intermediate or high risk disease will undergo definitive therapy including either surgery or radiation, but advanced age and comorbidities are known to influence the choice of primary treatment. In one series of over 11,000 patients, 4% of those over age 75 underwent surgery as primary therapy compared to 60% of patients under the age of 75. [4] Patients who are elderly or who have multiple medical illnesses are more likely to receive external beam radiation than younger, healthier men.[5]

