Due to the significant toxicities associated with ADT, and the uncertain benefit in the setting of dose escalation, the role of ADT in the elderly and in patients with significant comorbidities is particularly unclear. Some question the role of further testosterone suppression in elderly men in whom up to 80% meet the criteria for hypogonadism before treatment.[17] Furthermore, the elderly may have heightened sensitivity to the adverse effects of ADT resulting in more severe quality of life detriment than in younger patients. In a randomized trial from Harvard showing an overall survival benefit with the addition of short-term ADT to radiation in intermediate and high risk patients, a post-randomization analysis revealed a significant interaction between

comorbidity score and the effect of ADT on survival. In patients with moderate or severe comorbidities, the survival benefit to adding ADT to radiation was lost. [18] The lack of benefit to ADT seen in some groups may in part be due to hastening of cardiovascular disease, and thus death due to causes other than prostate cancer. Furthermore, given the long natural history of prostate cancer, the beneficial effects of ADT may be masked by competing causes of mortality in aging and unhealthy populations who are unlikely to benefit from aggressive therapy.

However, there is some clinical evidence in support of the use of ADT even in the elderly or those with significant comorbidities. A reanalysis of the Radiation Therapy Oncology Group (RTOG) 85-31 trial comparing ADT until progression versus no ADT in patients treated with radiation for high risk non-bulky disease, there was no impact of hormonal therapy on the risk of cardiovascular mortality.[19] In the Harvard randomized study of radiation with or without short term ADT, of 206 patients enrolled, there were 78 with mild or no comorbidity who were over the age of 72. Among the 70% of these men who were healthy, all cause mortality at 8 years was 16% in those treated with ADT plus radiation compared to 41% in those receiving radiation alone.[20] More investigation is warranted to clarify the risks and benefits of ADT in addition to radiation in patients with medical comorbidities and advanced age in order to improve patient selection.

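### Section 9.3 uses Kaplan-Meier for every oncologic endpoint and gives death no role in biochemical progression-free survival, so the curve fits neither the risk of PSA failure nor true progression-free survival

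*Combined protocol and SAP*

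**What the plan says.** Section 9.3 names four oncologic endpoints: "biochemical progression-free survival, distant metastasis-free survival, cause specific survival, and overall survival". For all of them the plan is the same: "Kaplan-Meier curves will be generated for each endpoint". Only the first is defined: "Biochemical progression free survival will be defined to be the time from the start of therapy with oral androgen manipulation until PSA failure occurs", with failure by the Phoenix criterion. Death is not mentioned in that definition as an event, a competing event or a reason for censoring. Distant metastasis-free survival and cause-specific survival have no definition, and no cumulative-incidence or other competing-risk method appears in the document.

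Section 9.3 also plans a Cox model for PSA failure against the control cohort, with the qualification "but formal statistical conclusions will not be drawn from this analysis".

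The population is described in section 1.1 as "prostate cancer patients 70 years of age or older and/or with moderate to severe medical comorbidities". Section 2.1 says that weighing benefit against toxicity in men with limited life expectancy is "clouded by competing risks of mortality related to comorbid illnesses and aging", and section 2.2 adds that "the beneficial effects of ADT may be masked by competing causes of mortality in aging and unhealthy populations".

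**The concern.** The background treats death from other causes as central to this population, yet the analysis section gives it no role. Two problems follow, with opposite signs.

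- **Against the probability of PSA failure or prostate-cancer death.** Kaplan-Meier treats a censored man as still able to fail later. A man who has died of something else cannot. One minus Kaplan-Meier then estimates risk in a hypothetical setting without other deaths, and exceeds the share of men who actually fail.
- **Against progression-free survival as the name is usually read.** That endpoint counts failure or death. Leaving death out makes event risk too low.

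Section 2.2 intends the data to lead to a larger randomized phase II study and possibly a phase III study. A failure rate carried forward without a clear statement of what it measures could be misread when those studies are planned.

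**Working it through.** **The plan's own figure.** Section 9.3 states no numerical target for these endpoints. The only design precision figure is in section 9.2, plus or minus 15% for a success rate of 0.6 with 40 men. It reproduces, 1.96 × √(0.6 × 0.4 / 40) = 0.152, but it concerns the quality-of-life endpoint and does not bear on this point.

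**Inputs.**
- Death hazard: section 2.2 cites 8-year all-cause mortality of 16% and 41% in the two arms of a randomized trial, among healthy older men. As constant hazards, −ln(0.84)/8 = 0.0218 per year and −ln(0.59)/8 = 0.0660 per year. These stand in for death without PSA failure.
- Times: month 28 (2.333 years), the end of protocol follow-up, and month 64 (5.333 years), five years after radiation. Section 4.6 only encourages the latter; section 7 makes follow-up beyond month 10 recommended, not required.
- PSA failure: the documents give no expected rate. **Assumption:** a Kaplan-Meier failure estimate of 30% at each time. The failure hazard is then −ln(0.70)/t: 0.1529 per year for month 28 and 0.0669 for month 64.

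**Formulas**, with constant failure hazard a and death hazard d:
- one minus Kaplan-Meier, deaths censored: 1 − exp(−a t)
- failure or death: 1 − exp(−(a + d) t)
- cumulative incidence of failure: a/(a + d) × [1 − exp(−(a + d) t)]

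**Worked example.** Month 28, d = 0.0660: a + d = 0.2188; failure or death = 1 − exp(−0.2188 × 2.333) = 0.400; a/(a + d) = 0.699; cumulative incidence = 0.699 × 0.400 = 0.279.

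| Time | d per year | 1 − KM | Cumulative incidence | Overstatement (points) | Failure or death |
|---|---|---|---|---|---|
| Month 28 | 0.0218 | 30% | 29.3% | 0.7 | 33.5% |
| Month 28 | 0.0660 | 30% | 27.9% | 2.1 | 40.0% |
| Month 64 | 0.0218 | 30% | 28.4% | 1.6 | 37.7% |
| Month 64 | 0.0660 | 30% | 25.6% | 4.4 | 50.8% |

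Read as failure or death, the PSA-only figure of 30% is therefore too low by 3.5 to 10.0 points at month 28 and 7.7 to 20.8 points at month 64.

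**Range over assumptions.** Doubling the higher death hazard to 0.132 per year (assumed, for sicker men) gives cumulative incidences of 26.1% and 22.0%, overstatements of 3.9 and 8.0 points. If instead the five-year failure risk without competing death is assumed to lie between 10% and 40%, with the cited mortality, the overstatement is 0.1 to 1.5 points at month 28 and 0.6 to 6.0 points at month 64.

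**Sampling error for scale** (complete follow-up, risk of 30%). One cohort of 40: 1.96 × √(0.21/40) = 14.2 points. Difference between 40 and 30 men: 1.96 × √(0.21/40 + 0.21/30) = 21.7 points. If one cohort had the lower death hazard and the other the higher, the overstatements at month 28 would differ by 2.1 − 0.7 = 1.4 points.

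**The case against.** The case for leaving the plan alone is substantial. This is a feasibility study with a quality-of-life primary endpoint. The oncologic endpoints are secondary, and the Cox comparison of PSA failure is expressly non-inferential. Within protocol follow-up the overstatement is a small fraction of sampling error, and the larger values need follow-up that is only encouraged. The inputs are rough: the mortality figures are all-cause, so they include cancer deaths; the 41% comes from radiation alone, which neither cohort here receives; and the men were healthy, whereas this trial also admits men with a Charlson score of 2 or more. The proxy could be too high or too low. The plan never writes that deaths are censored; that is inferred from the definition. A Cox model for PSA failure with deaths censored already estimates a cause-specific hazard ratio, a legitimate quantity.

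All of this stands and limits the size of the point. It does not remove it: the name and definition of biochemical progression-free survival still disagree, and cumulative incidence answers the question of how many men fail, from the same data.

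A reader might infer two stronger things, and the documents support neither.

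- **That metastasis risk is overstated too.** Distant metastasis-free survival is undefined. If death counts as an event, as the name suggests, Kaplan-Meier is valid. The gap there is the missing definition.
- **That the estimator can create or hide a difference between cohorts.** Controls must meet the same eligibility criteria (section 4.3). Without randomization their mortality may differ, but nothing shows by how much or in which direction, and 1.4 points at month 28 is far inside a half-width of about 22.

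**Conclusion.** The point holds as a minor one. Followed as written, section 9.3 yields an endpoint called progression-free survival that takes no account of death. If deaths are censored, it also yields overstated probabilities of PSA failure and, through cause-specific survival, of prostate-cancer death. For PSA failure the overstatement is about 0.7 to 2.1 points at month 28 and 1.6 to 4.4 points at month 64. Against a true failure-or-death endpoint the error reverses and is larger, so it would be wrong to say simply that event risk is overstated; the sign depends on the quantity wanted.

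These sizes rest on constant and independent hazards, the cited all-cause mortality as a proxy, and the assumed 30%. No corresponding size is given for prostate-cancer death, because the documents state no rate for it. Overall survival is unaffected.

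**What to change.** In section 9.3, state the event and the handling of death for each endpoint:

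- **Biochemical progression-free survival:** either count death from any cause as an event and keep Kaplan-Meier, or rename it time to PSA failure and estimate cumulative incidence (Aalen-Johansen) with death without failure as the competing event.
- **Prostate-cancer death:** estimate cumulative incidence, with other-cause death as the competing event.
- **Distant metastasis-free survival:** state that death counts as an event; Kaplan-Meier is then valid.
- **Overall survival:** keep Kaplan-Meier.
- **Cox model for PSA failure:** keep it, and label the result a cause-specific hazard ratio if deaths are censored.

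The cost is a few sentences and standard software, with no extra patients or visits. Dates and causes of death are needed, but the planned survival endpoints already require them. Counting death in biochemical progression-free survival does change the endpoint, so the choice should be made and recorded before the data are analyzed.

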#### **4.4. General Concomitant Medication and Supportive Care Guidelines**

Development of painful mastitis and gynecomastia are potential side effects of antiandrogen therapy in the absence of gonadal suppression. There is no restriction towards the use of radiation for the prophylaxis or treatment of breast tenderness or gynecomastia. Patients should not receive Tamoxifen or other estrogen modulating therapy during treatment on the trial given concern for unknown effects on the hormonal milieu. Treatment with breast radiation to breast tissue should be clearly documented for each patient in whom it is employed. If prophylactic or therapeutic intervention is sought, a dose of 12 Gy in 3 fractions using en face electrons is preferred.

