### 6.3. Data and Safety Monitoring

A weekly meeting in the department of radiation oncology will be held for data and safety monitoring of patients enrolled at the University of Chicago site.

The primary endpoint, HRQOL, will be formally evaluated at 6 months.

Stopping rules include excessive failures defined by biochemical failure in > 70% of patients at 2 years or excessive toxicity defined as >15% of patients with acute or late Grade 3+ toxicity.

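### Biochemical progression counts only a PSA rise to nadir+2, so earlier salvage therapy is not an event, and its clock does not exist for controls

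*Combined protocol and SAP*

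**What the plan says.** Section 9.3 holds the only definition. The endpoint is "the time from the start of therapy with oral androgen manipulation", and it runs "until PSA failure occurs as defined by the Phoenix definition of a rise to 2 ng/ml above the nadir PSA value". No other event is named and there is no censoring rule. The section plans Kaplan-Meier curves for each oncologic endpoint and adds: "Findings will be compared to a synchronous cohort of controls". A Cox model is to estimate "The relative hazard for a PSA failure in patients on protocol therapy compared to those in the control cohort", with the caveat that "formal statistical conclusions will not be drawn from this analysis".

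Other sections bear on it as follows.

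- **Sections 1.1 and 4.3:** controls receive a GnRH agonist with or without an antiandrogen. Their follow-up and laboratory tests lie outside the protocol, although their medical records may be used.
- **Section 4.4:** "Patients should not receive Tamoxifen or other estrogen modulating therapy during treatment on the trial". This concerns breast symptoms. Nothing there addresses later hormonal therapy for a rising PSA.
- **Sections 4.5 and 4.7:** the removal criteria name neither progression nor salvage.
- **Section 6.3:** "Stopping rules include excessive failures defined by biochemical failure in > 70% of patients at 2 years".
- **Section 7:** current medicines are documented at every visit, but visits after month 10 are recommended rather than required.
- **Section 8:** covers PSA testing and clinical examination, and gives no salvage rule.

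**The concern.** Hormonal therapy lowers PSA. Section 2.2 itself cites a study of men with rising PSA after surgery or radiation in whom oral combination therapy cut PSA by 80% in 98.6% of patients. A man given such treatment while his PSA is rising but still below nadir+2 may not reach that level during study follow-up. Read literally, section 9.3 then carries him as progression-free although his physician has judged that the first treatment failed.

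The second gap is the clock. It is tied to the experimental drugs, so the planned comparison with controls needs a start date that the plan does not supply.

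At stake are the failure estimates and the secondary objective in section 1.2, that oncologic outcomes are comparable with standard ADT. Section 2.2 also foresees a larger phase II study and possibly a later non-inferiority study, for which these failure rates would be a natural planning input.

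**Working it through.** **1. Is there a plan figure to reproduce?** Not for this endpoint: no hazard ratio, event count, power or margin is given. The only precision figure, in section 9.2, is about ±15 points for a success rate of 0.6 with n = 40, on the hormonal/vitality score. It reproduces: 1.96 × √(0.6 × 0.4 / 40) = 0.152. It does not depend on the present point.

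**2. Effect on the failure estimate.** Input from section 9.2: 40 experimental men. Assumptions, since the documents give neither: true 2-year failure f of 10%, 20% or 30%, and a fraction k of failures (10%, 25%, 50%) salvaged before nadir+2 and never counted. Counted failures = 40 × f × (1 − k).

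| True f (men of 40) | k = 10% | k = 25% | k = 50% |
|---|---|---|---|
| 10% (4) | 3.6 (9%) | 3.0 (7.5%) | 2.0 (5%) |
| 20% (8) | 7.2 (18%) | 6.0 (15%) | 4.0 (10%) |
| 30% (12) | 10.8 (27%) | 9.0 (22.5%) | 6.0 (15%) |

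**3. Would censoring at salvage repair it?** No. With a constant hazard, apparent failure is 1 − (1 − f)^(1 − k). For f = 20% this gives 18.2%, 15.4% and 10.6%, almost the same shortfall. Such censoring is informative.

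**4. Effect on the hazard ratio.** Apparent HR ≈ true HR × (1 − k in the oral cohort) / (1 − k in controls). With a true HR of 1:

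- oral cohort only, k = 25% or 50%: 0.75 or 0.5;
- controls only, k = 25% or 50%: 1/0.75 = 1.33 or 1/0.5 = 2.0;
- equal k in both cohorts: 1.0.

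The direction depends entirely on which cohort has more early salvage, and the documents do not say.

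**5. Effect of the time origin.** Suppose the control clock began 2 months after hormone start (at the start of radiation) or 4 months after (at its end). Month 24 on that clock is then month 26 or 28 from hormone start. With f = 20% and a constant hazard, 1 − 0.8^(26/24) = 21.5% and 1 − 0.8^(28/24) = 22.9%, against 20%.

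**6. Effect on the stopping rule.** More than 70% of 40 men means at least 29. The largest true count in the table is 12. Undercounting matters to the rule only if true failures already number 29 or more.

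**The case against.** The best case for leaving the text alone has several parts.

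- **Inference.** The study is a feasibility trial of quality of life, and section 9.3 disclaims formal conclusions from the Cox model. With 10% failure in 40 and 30 men there would be about 4 and 3 events. SE(log HR) = √(1/4 + 1/3) = 0.76, so an HR of 1 would have a 95% interval of about 0.22 to 4.5. This stands and limits the weight of the point. The disclaimer, however, covers only the Cox analysis and not the Kaplan-Meier curves.
- **Existing data.** Medicines are documented at visits, and distant metastasis-free, cause-specific and overall survival are separate endpoints. This stands too, and makes the change cheap. But the reason for a new drug is not recorded, and none of those endpoints captures early salvage.
- **Removal from study.** A salvaged man might be removed under section 4.7 and censored. The text does not say so, and step 3 shows that censoring would not help.
- **Control clock.** Section 4.3 uses the start of standard ADT for the early control questionnaires, so the intended origin could be guessed. The same section anchors the later ones to the start of radiation, so the guess is not secure. The numerical effect is small either way.

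A reader might infer that a salvaged man can never fail. He still counts if his PSA later reaches nadir+2. A reader might also infer that the definition flatters oral therapy. That needs more early salvage in the oral cohort than in controls, whereas prolonged ADT in controls could suppress their PSA and push the ratio the other way.

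**Conclusion.** The gap is real. Salvage before nadir+2 has no place in the definition, and controls have no stated start date. The loss to a failure estimate equals the share of failures salvaged early: in the illustration, a true 20% reads as 18% to 10% for shares of 10% to 50%. Those shares, and the 2-year failure rates, are assumptions. The size and direction of any bias between cohorts are unknown. The clock mismatch alone is worth about 1.5 to 3 points at a 20% failure rate.

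It would be tempting to conclude that the biochemical-failure stopping rule is undermined. The documents do not support that: the threshold is too high to be moved in practice, and section 6.3 does not refer to the definition in section 9.3.

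Because the endpoint is secondary and the Cox comparison descriptive, this is a minor-to-moderate point, confined to the failure estimates and the comparability objective.

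**What to change.** In section 9.3:

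- Time the endpoint in both cohorts from the first dose of any hormonal therapy.
- Define the event as the earliest of nadir+2 or the start of new or resumed non-protocol hormonal therapy or local salvage, given for documented rising PSA or progression.
- Keep nadir+2 alone as a sensitivity analysis.
- Record the date and reason for any such therapy, from the chart for controls.
- Do not count prolonged ADT in a control as an event unless his intended duration was recorded at baseline. The protocol states no control duration against which to judge it.

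**Cost:** analysis wording and a case-report entry for date and reason. Reported failure rates may be slightly higher. Salvage is also a discretionary event and may be ascertained differently in controls, whose follow-up is outside the protocol; the sensitivity analysis shows how far the result depends on it. No treatment rule and no sample size changes.

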### **1.2. Secondary Objectives**

The secondary objective is to test the hypothesis that oncologic outcomes including biochemical progression free survival, distant metastasis free survival, cause specific survival, and overall survival after treatment with dual oral androgen manipulation and dose escalated radiation will be comparable to the outcomes of patients treated with standard ADT.

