### **3. PATIENT SELECTION**

#### **3.1. Eligibility Criteria**

3.1.1. Age  $\geq$  70 years

AND/OR

Charlson comorbidity index score  $\geq$  2 (see Appendix C)

(Prostate cancer diagnosis does not contribute to total score)

3.1.2. Pathologically (histologically) proven diagnosis of prostatic adenocarcinoma.

3.1.3. Intermediate or high risk for recurrence according to the following criteria:

Two or more of the following intermediate risk features for recurrence

- Gleason Score = 7
- PSA 10-20 ng/ml
- Clinical Stage T2b-T2c
- Percent positive biopsy cores  $\geq 50\%$

**OR**

One or more of the following high risk features for recurrence

- Gleason Score 8-10
- PSA >20 ng/ml
- Clinical Stage T3a-T4

3.1.4. Clinically negative lymph nodes as established by imaging (pelvic +/- abdominal CT or MRI), nodal sampling, or dissection, except as noted immediately below:

- Patients with intermediate risk factors only do not require abdominopelvic imaging, but these studies may be obtained at the discretion of the treating physician.
- For men with any high risk feature (psa > 20, gleason score >8, or clinical stage T3), a pelvic CT or MRI, are required. It is recommended that the duration between these scans and study registration be less than 60 days, but if the time period is >60 days and the opinion of the clinician is that repeat studies would offer limited benefit, then these studies do not need to be repeated. A lymph node will be considered radiographically positive if it is >1.5cm in size, occurs within the expected distribution for prostate cancer metastasis (i.e. internal iliac or obturator fossa), and is without classic benign features (i.e. fatty hilum). Patients with lymph nodes equivocal or questionable by imaging are eligible for inclusion in this study.

3.1.5. No evidence of bone metastases (M0) on bone scan.

- Patients with intermediate risk factors only do not require a bone scan, but these studies may be obtained at the discretion of the treating physician.
- Patients with any high risk factors are required to undergo a bone scan. It is recommended that the duration between these scans and study registration be less than 60 days, but if the time period is >60 days and the opinion of the clinician is that repeat studies would offer limited benefit, then these studies do not need to be repeated.
- Equivocal bone scan findings are allowed if additional imaging (e.g. plain film x-rays, or CT) does not confirm metastasis.

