#### **4.3. Experimental Controls**

Patients who meet eligibility criteria of the study but who do not enroll on the trial who receive standard ADT with radiation will be approached for participation in the parallel data collection study. These patients will serve as the control group with which to compare HRQOL outcomes of patients treated on trial. Patients consenting to enrollment on the parallel data collection study will receive standard of care treatment, follow-up, imaging, and laboratory studies not subject to the plan described in this protocol. Health information may be recorded from the electronic medical record. Patients on the data collection study will be asked to complete the same supplemental four-page questionnaire (see Appendix B) as those on trial at baseline, 1-2 months after initiation of standard ADT (before RT), and at 6 months. Completion of the supplemental questionnaire will not be required at 12, 18, and 24 months after initiation of radiation, however any collected data over this time frame will be recorded and available for analysis. In addition, all controls will complete the six-page questionnaire which is standard practice for all patients treated in the department of radiation oncology according to usual practice.

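### Section 9.3 names no risk-group adjustment for its oncologic comparisons between non-randomized cohorts of mixed risk (minor: few events, and the Cox result is already disclaimed)

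*Combined protocol and SAP*

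**What the plan says.** All references are to the combined protocol and SAP.

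- **Section 9.3, curves.** For biochemical progression-free, distant metastasis-free, cause-specific and overall survival: "Kaplan-Meier curves will be generated for each endpoint. Findings will be compared to a synchronous cohort of controls".
- **Section 9.3, hazard ratio.** "The relative hazard for a PSA failure in patients on protocol therapy compared to those in the control cohort will be calculated using" Cox regression, with the qualification "but formal statistical conclusions will not be drawn from this analysis". No covariate, stratification, matching or weighting is mentioned for the curves or the model.
- **Section 9.1.** Quality-of-life and toxicity scores are compared by t-test and also by linear regression that controls for covariates, which are not listed. This adjustment is stated for scores only.
- **Section 4.3.** Controls are "Patients who meet eligibility criteria of the study but who do not enroll on the trial who receive standard ADT with radiation". Their stated purpose is narrower than the use in 9.3: "These patients will serve as the control group with which to compare HRQOL outcomes of patients treated on trial".
- **Section 3.1.3.** A man qualifies with "Two or more of the following intermediate risk features for recurrence" or with at least one high-risk feature. There is no quota or balancing rule for either group.
- **Section 1.2.** "The secondary objective is to test the hypothesis that oncologic outcomes including biochemical progression free survival, distant metastasis free survival", cause-specific and overall survival will be comparable to standard ADT. No margin, error rate or power is given.

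**The concern.** Section 3.1.3 defines its two groups by risk of recurrence, so by the plan's own terms risk group should predict PSA failure. Membership of a cohort depends on whether a man enrolls, not on chance. If the share of high-risk men differs between cohorts, the unadjusted curves and hazard ratio combine that difference with any effect of treatment. Fewer high-risk men in the oral cohort would flatter oral therapy and could hide a real loss of disease control. More would make it look worse than it is.

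The analyses address the comparability objective in section 1.2. The plan shows awareness of confounding for scores in 9.1 but makes no matching provision in 9.3, although the eligibility check already establishes the risk group.

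**Working it through.** **1. The plan's own figure.** The only precision figure is in section 9.2: about 15 points either side for a success rate of 0.6 with 40 men. It reproduces: 1.96 × √(0.6 × 0.4 / 40) = 0.152. It concerns the primary proportion. No event count, power or margin is given for an oncologic endpoint.

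**2. Inputs.** From the documents: 40 oral and 30 control men. Assumed, because the documents give no values: no treatment effect; PSA-failure hazard of 2% per year in intermediate-risk men; h = 2 to 4 times that in high-risk men; two years of observation; high-risk share f of 40% (oral) v 60% (control), or 30% v 70%.

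**3. Formulas.**
- Two-year failure-free proportion: S(f) = (1 − f)·exp(−0.04) + f·exp(−0.04h)
- Crude hazard ratio: ln S(oral) / ln S(control)
- Expected failures: D = 40·(1 − S(oral)) + 30·(1 − S(control))
- SE of the log hazard ratio: 1/√(D × 40/70 × 30/70). The 95% interval multiplies and divides the estimate by exp(1.96·SE).

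**4. One case in full (40% v 60%, h = 2).**
- S(oral) = 0.6 × 0.9608 + 0.4 × 0.9231 = 0.9457; S(control) = 0.4 × 0.9608 + 0.6 × 0.9231 = 0.9382.
- Crude hazard ratio = 0.0558/0.0638 = 0.87.
- D = 2.17 + 1.85 = 4.0; SE = 1.01; interval factor = 7.2.
- Bias = |ln 0.87|/1.01 = 0.13 SE.

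**5. Range under no treatment effect.**

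| High-risk share, oral v control | h | Crude HR | Expected failures | 95% factor each way | Bias in SEs |
|---|---|---|---|---|---|
| 40% v 60% | 2 | 0.87 | 4.0 | 7.2 | 0.13 |
| 40% v 60% | 3 | 0.82 | 5.3 | 5.6 | 0.23 |
| 40% v 60% | 4 | 0.78 | 6.4 | 4.8 | 0.31 |
| 30% v 70% | 2 | 0.76 | 4.0 | 7.3 | 0.27 |
| 30% v 70% | 3 | 0.66 | 5.2 | 5.7 | 0.46 |
| 30% v 70% | 4 | 0.61 | 6.3 | 4.8 | 0.62 |

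Reversing the imbalance gives 1.14 (60% v 40%, h = 2) to 1.64 (70% v 30%, h = 4), with 4.1 to 6.8 failures. The two-year curves differ by 0.8 to 4.3 points.

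**6. A higher failure rate.** If 90% of intermediate-risk men are failure-free at 28 months and h is 2 to 3, about 10 to 13 failures are expected. With 10, the interval factor is 3.5 and power to detect a hazard ratio of 2 is 19%.

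**7. How easily an imbalance could arise.** If half of all men are high-risk, the chance SD of the difference in share is √(0.25/40 + 0.25/30) = 0.121. A gap of 20 points or more would then occur about 10% of the time even under random allocation.

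**8. Does stratification help with so few events?** Simulated trials of 40 v 30 men, no treatment effect, h = 3, 28 months, about 13 failures, using crude and risk-stratified log-rank (one-step) estimates of the log hazard ratio:

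| Share | Mean, crude | Mean, stratified | Median SE, crude → stratified | RMSE, crude → stratified |
|---|---|---|---|---|
| 40% v 60% | about −0.2 | 0.00 | 0.56 → 0.57 | 0.62 → 0.59 |
| 30% v 70% | −0.43 | 0.00 | 0.57 → 0.61 | 0.73 → 0.63 |

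With about 6 failures, stratification still removed the bias and lowered the RMSE.

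**9. Curves within risk group.** At 2% per year and the shares in step 5, the four cohort-by-risk cells expect about 0.35 to 3.1 failures each. The intermediate-risk control cell holds 12 or 9 men, so its chance of no failure is exp(−0.04 × 12) = 0.62 or exp(−0.04 × 9) = 0.70.

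**The case against.** The strongest reply is that little rests on this analysis. Section 9.1 calls the trial a feasibility study leading to a randomized comparison, section 8 says disease control is not the primary endpoint, and section 4.3 recruits controls for quality of life. The biochemical-failure stopping rule in section 6.3 uses a single proportion, not a comparison with controls. Section 9.3 disclaims formal conclusions from the Cox model. With 4 to 6 failures, the assumed bias is 0.13 to 0.62 SE, so no reader should take the hazard ratio as evidence in either direction. Section 7 makes follow-up after month 10 recommended rather than required, so events could be fewer still.

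Most of this stands, and it limits the severity. Two parts of the point remain. The disclaimer is attached to the Cox analysis, not to the Kaplan-Meier comparisons, and section 1.2 still speaks of testing a hypothesis. Also, wide intervals do not justify leaving in a systematic shift that one stratification term removes at little cost.

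A reader might infer more than the documents support:
- **That the Cox model has cohort as its only term.** Section 9.3 is silent; it names no other term but excludes none.
- **That controls declined the trial, or that high-risk men are steered into standard ADT.** Section 4.3 says only that controls do not enroll. It gives no reason and no direction of selection.
- **That risk features are certain to be in the research record for every control.** Controls must meet eligibility, so the information exists, but section 4.3 says only that their health information may be recorded.

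**Conclusion.** The concern holds as a minor point. Section 9.3 names no adjustment for an obvious prognostic factor in a non-randomized comparison, while 9.1 provides for adjustment of scores. Under no treatment effect, the assumed imbalances give a crude hazard ratio of 0.87 to 0.61, or 1.14 to 1.64 in the other direction. These are assumption ranges, not predictions: the risk shares, the high-risk hazard ratio and the failure rate are all absent from the documents.

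A reader might go further and conclude that case mix alone would pass for a treatment effect. That is not supported. Random error exceeds the bias in every case tabulated, and the plan already withholds formal conclusions from the Cox result. The defect is an avoidable bias in a descriptive result, together with a label that does not cover the curves and an objective worded more strongly than the analysis allows.

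**What to change.** In section 9.3:
1. Stratify the Cox model by the 3.1.3 risk group (intermediate features only v any high-risk feature). Report it beside the crude hazard ratio, with confidence intervals and event counts for each cohort.
2. Tabulate the risk-group split of each cohort next to the Kaplan-Meier curves, and make sure the risk group is recorded for controls.
3. Extend the statement that no formal conclusions will be drawn to the Kaplan-Meier comparisons.

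In section 1.2, and where the schema repeats it, reword the secondary objective as descriptive.

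Kaplan-Meier curves within risk group should be optional, because some strata would probably have no events.

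The cost is a few sentences and information already needed for eligibility. The SE rises by roughly 1% to 7% in the simulated cases. Stratification does not correct other differences: control follow-up and laboratory work lie outside the protocol schedule (4.3), and the time origin in 9.3, the start of oral androgen manipulation, is undefined for controls. The stratified result should therefore not be presented as free of confounding.
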